13.2.3 OCULUS KERATOGRAPH

Oculus keratography will be assessed at all visits at selected sites only. Only pre-CAE® assessments will be made at Visits 1 and 5. First break (seconds), average time (seconds) and tear meniscus height (mm) will be recorded.

Oculus keratography measurements will be summarized by treatment group and visit using quantitative summary statistics. Change from baseline will be also summarized.

Pairwise two-sample t-tests will be employed to compare treatment and vehicle means at each visit and time point. The differences in means, two-sided 95% CIs for the difference in means and p-values will be reported. Wilcoxon rank sum tests will also be conducted. Analyses will be performed on the mITT population with observed data only.

Changes from baseline will be compared between treatment groups using ANCOVA models that adjust for baseline value, baseline inferior corneal staining (Ora Calibra® scale) and baseline eye dryness (VAS). The differences in means, two-sided 95% CIs for the difference in means and p-values will be reported. T-tests and Wilcoxon rank sum tests will also be conducted. Analyses will be performed on the mITT population with observed data only.

13.2.4 CONJUNCTIVAL REDNESS SCORE

The Ora Calibra® Conjunctival Redness Scale for Dry Eye will be performed on all scheduled visits. Both pre- and post-CAE® assessments will be made at Visits 1 and 5. The conjunctival redness scale ranges from 0 to 4 where 0 = normal, without vasodilation, 1 = trace ciliary or conjunctival vasodilation, 2 = broad ciliary vasodilation, 3 = broad ciliary and slight, horizontal conjunctival vasodilation, and 4 = broad ciliary and prominent, horizontal conjunctival vasodilation. Half unit increments are allowed.

Conjunctival redness will be summarized by treatment group, visit and time point (pre- and post-CAE®) using quantitative summary statistics. Change from baseline will be also summarized.

Pairwise two-sample t-tests will be employed to compare treatment and vehicle means at each visit and time point. The differences in means, two-sided 95% CIs for the difference in means and p-values will be reported. Wilcoxon rank sum tests will also be conducted. Analyses will be performed on the mITT population with observed data only.

Changes from baseline will be compared between treatment groups using ANCOVA models that adjust for baseline value, baseline inferior corneal staining (Ora Calibra® scale) and baseline eye dryness (VAS). The differences in means, two-sided 95% CIs for the difference in means and p-values will be reported. T-tests and Wilcoxon rank sum tests will also be conducted. Analyses will be performed on the mITT population with observed data only.

A binary clinical cure variable will be defined by visit for conjunctival redness = 0, and will be summarized by visit using number of subjects, frequency counts and percentages. Treatment groups will be compared pairwise with vehicle using Pearson's chi-square test or Fisher's exact test if the expected cell count is less than 5 in 25% or more of the cells. In addition, the proportion of responders will be compared between treatment groups using the Cochran-Mantel-Haenszel method stratifying by baseline ICSS (≤ 1.5 , > 1.5) and baseline eye dryness (< 60 , ≥ 60). For the Cochran-Mantel-Haenszel

analysis of the combined Stage 1 and Stage 2 data, the study Stage will also be included as a stratification factor.

13.2.5 FLUORESCEIN CORNEAL STAINING (ORA CALIBRA® SCALE)

Corneal and conjunctival fluorescein staining will be performed at all scheduled visits, on both eyes and graded using the Ora Calibra® Corneal and Conjunctival Staining Scale. Both pre- and post-CAE® assessments will be made at Visits 1 and 5. The scale will grade the cornea and conjunctiva by five regions: inferior, superior, central, temporal, and nasal. The Ora Calibra® Corneal and Conjunctival Staining Scale ranges from 0 to 4 (half grade increments may be used), where grade 0 = none, 1 = trace, 2 = mild, 3 = moderate, and 4 = severe.

Fluorescein staining scores will be summarized by treatment group, visit, time point (pre- and post-CAE®), and region (5 regions, plus corneal sum, conjunctival sum, and total scores) for the study eye using quantitative summary statistics. The corneal sum score will be the sum of scores from the inferior, superior, and central regions. The conjunctival sum score will be the sum of scores from the nasal and temporal regions. The total score will be the sum of scores from all five regions.

Pairwise two-sample t-tests will be employed to compare treatment and vehicle means at each visit and time point. The differences in means, two-sided 95% CIs for the difference in means and p-values will be reported. Wilcoxon rank sum tests will also be conducted. Analyses will be performed on the mITT population with observed data only.

Changes from baseline will be compared between treatment groups using ANCOVA models that adjust for baseline value, baseline inferior corneal staining (Ora Calibra® scale) and baseline eye dryness (VAS). The differences in means, two-sided 95% CIs for the difference in means and p-values will be reported. T-tests and Wilcoxon rank sum tests will also be conducted. Analyses will be performed on the mITT population with observed data only.

Binary clinical cure variables will be defined by visit and region for clearing (score = 0) and 1-unit improvement (change from baseline ≤ -1), and will be summarized by visit and region using number of subjects, frequency counts and percentages. Treatment groups will be compared pairwise with vehicle using Pearson's chi-square test or Fisher's exact test if the expected cell count is less than 5 in 25% or more of the cells. In addition, the proportion of responders will be compared between treatment groups using the Cochran-Mantel-Haenszel method stratifying by baseline ICSS (≤ 1.5 , > 1.5) and baseline eye dryness (< 60 , ≥ 60). For the Cochran-Mantel-Haenszel analysis of the combined Stage 1 and Stage 2 data, the study Stage will also be included as a stratification factor.

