7 STUDY POPULATION

7.1 Number of Subjects (approximate)

Stage 1:

The total number of randomized patients for Stage 1 of the study will be approximately 100 at up to 2 sites. Approximately 50% of patients should have a baseline eye dryness score of ≥ 60 and approximately 50% of patients should have a baseline inferior corneal staining score (ICCS) > 1.5 according to the Ora Calibra[®] staining scale. Based upon data from Xiidra[®], OPUS 2 a screen failure rate of $\sim 50\%$ is expected. Thus, ~ 200 patients will need to be screened to achieve ~ 100 patients randomized to treatment.

Stage 2:

The total number of randomized patients for Stage 2 of the study will be approximately 330 (see [Figure 6.1-1](#), Stage 2) at up to 7 sites. Approximately 50% of patients should have a baseline eye dryness score of ≥ 60 and approximately 50% of patients should have a baseline inferior corneal staining score (ICCS) > 1.5 according to the Ora Calibra[®] staining scale. Based upon data from Xiidra[®], OPUS 2 a screen failure rate of $\sim 50\%$ is expected. Thus, ~ 660 patients will need to be screened to achieve ~ 330 patients randomized to treatment.

Note: patients can be reallocated from discontinued groups to increase the power in groups that are continued at the discretion of the DRC.

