7.3 Inclusion Criteria

1. Male or female, 18 years of age or older at screening visit
2. Provide written informed consent
3. Be willing and able to follow instructions and participate in all study assessments and visits
4. Best-corrected visual acuity (BCVA) of 20/100 or better (Snellen equivalent), using the logarithm of the minimum angle of resolution (LogMAR) in each eye at Visits 1 and 2
5. Must have patient reported history of dry eye for at least 6 months prior to Visit 1
6. Use of non-prescription artificial tears for the symptoms of DED within the 30 days preceding the screening visit and willing to suspend use of artificial tears for the study duration
7. Corneal fluorescein staining score ≥ 2 according to the Ora Calibra[®] scale in at least one region in at least one eye at the screening Visit 1 (Pre-CAE[®]) and Visit 2
8. Conjunctival redness score ≥ 1 according to the Ora Calibra[®] Conjunctival Redness for Dry Eye Scale in at least one eye at Visit 1 (Pre-CAE[®]) and Visit 2
9. Eye dryness score ≥ 40 (0-100 VAS scale in both eyes) at Visit 1 (Pre-CAE[®]) and Visit 2
10. Total Ocular Surface Disease Index (OSDI) score > 18 at Visit 1 (Pre-CAE[®]) and Visit 2
11. In the same eye at Visits 1 and 2, subjects must have:
 - a. Inferior corneal fluorescein staining score ≥ 0.5 according to the Ora Calibra[®] Corneal and Conjunctival Staining Scale for Grading of Fluorescein Staining, Pre-CAE[®] at Visit 1
 - b. Schirmer's Tear Test without anesthesia ≥ 1 and ≤ 10 mm

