13.2.6 FLUORESCEIN CORNEAL STAINING (OXFORD SCALE)

Corneal fluorescein staining will be performed at all scheduled visits and graded using the Oxford Scale. Both pre- and post-CAE® assessments will be made at Visits 1 and 5. The Oxford scale for corneal staining ranges from 0 to 5 for the corneal region, with higher scores indicating greater staining.

Staining scores will be summarized by treatment group, visit and time point (pre- and post-CAE®) using quantitative summary statistics. Change from baseline will be also summarized. Each region and total score will be summarized separately.

Pairwise two-sample t-tests will be employed to compare treatment and vehicle means at each visit and time point. The differences in means, two-sided 95% CIs for the difference in means and p-values will be reported. Wilcoxon rank sum tests will also be conducted. Analyses will be performed on the mITT population with observed data only.

Changes from baseline will be compared between treatment groups using ANCOVA models that adjust for baseline value, baseline inferior corneal staining (Ora Calibra® scale) and baseline eye dryness (VAS). The differences in means, two-sided 95% CIs for the difference in means and p-values will be reported. T-tests and Wilcoxon rank sum tests will also be conducted. Analyses will be performed on the mITT population with observed data only.

Binary clinical cure variables will be defined by visit and region for clearing (score = 0) and 1-unit improvement (change from baseline ≤ -1), and will be summarized by visit and region using number of subjects, frequency counts and percentages. Treatment groups will be compared pairwise with vehicle using Pearson's chi-square test or Fisher's exact test if the expected cell count is less than 5 in 25% or more of the cells. In addition, the proportion of responders will be compared between treatment groups using the Cochran-Mantel-Haenszel method stratifying by baseline ICSS (≤ 1.5 , > 1.5) and baseline eye dryness (< 60 , ≥ 60). For the Cochran-Mantel-Haenszel analysis of the combined Stage 1 and Stage 2 data, the study Stage will also be included as a stratification factor.

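### The regional 1-unit staining responder cannot be met from a baseline of 0 or 0.5 (Ora) or 0 (Oxford), and clearing is met by regions already at 0; both need a baseline-eligible denominator.

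*SAP*

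**What the plan says.** SAP 13.2.5 (fluorescein, Ora Calibra): "Binary clinical cure variables will be defined by visit and region for clearing (score = 0) and 1-unit improvement (change from baseline ≤ -1". SAP 13.2.6 (fluorescein, Oxford) repeats "1-unit improvement (change from baseline ≤ -1", and 13.2.7 (lissamine, Oxford) has the same rule. Each pair of variables is tabulated as counts and percentages. Arms are compared by Pearson chi-square or Fisher's exact test, and by CMH stratified on inferior staining (cut at 1.5) and eye dryness (cut at 60).

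The Ora scale "ranges from 0 to 4 (half grade increments may be used), where grade 0 = none". The Oxford scale runs from 0 to 5 per region. SAP 13.2.5 summarises staining by "region (5 regions, plus corneal sum, conjunctival sum, and total scores) for the study eye using quantitative summary statistics".

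Two staining thresholds govern entry (Protocol 7.3): "Inferior corneal fluorescein staining score ≥ 0.5 according to the Ora Calibra" in the qualifying eye, and "Corneal fluorescein staining score ≥ 2 according to the Ora Calibra" in at least one region of at least one eye. The superior, central, temporal and nasal regions have no individual minimum, and lissamine staining has none at all. Protocol 7.1 adds that "approximately 50% of patients should have a baseline inferior corneal staining score (ICCS) > 1.5".

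SAP 13.2 runs the secondary analyses on mITT with observed data, and SAP 7.1 gives mITT no staining minimum. The population limited to inferior scores above 1.5 (mITT2) is used for the primary analysis only. No separate denominator is stated for the staining responders.

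**The concern.** Some regions cannot satisfy the 1-unit definition whatever the treatment does, and others satisfy clearing with no change at all. Both sit in the denominator of every regional percentage. Three consequences follow:

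- The 1-unit percentages and their difference are pulled towards zero by an amount set by the baseline distribution, not by the drug.
- A lightly stained region shows a low 1-unit rate and a high clearing rate for the same reason, namely that it started near the floor. No between-region test is planned, but the percentages will be tabulated region by region and read that way.
- The chi-square, Fisher and CMH tests lose some power in a Phase 2 study that is looking for a signal.

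The planned stratification does not remove the affected regions. The CMH cut is at 1.5 rather than 1, and it uses the inferior score whichever region is being analysed.

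**Working it through.** **1. The plan's own figure.** SAP 5 gives 80% power for a 0.35 difference in inferior staining, SD 0.75, with 93 vs 60 subjects. SE = 0.75 × √(1/93 + 1/60) = 0.1242, and 0.35/0.1242 = 2.818. Normal approximation: Φ(2.818 − 1.960) = 80.5%; noncentral t on 151 df: 80.0%. Dropout: 103 × 0.9 = 92.7 and 67 × 0.9 = 60.3. The figure reproduces. It concerns a continuous primary variable; no responder variable is powered. Only the group sizes are used below.

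**2. Which baselines can respond.** A change of −1 or lower needs baseline − 1 ≥ 0. On the Ora scale 0 and 0.5 fail, while 1.0 to 4.0 can succeed. On the Oxford scale only 0 fails.

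**3. Effect on the estimates.** Let f be the share of eyes whose region cannot respond, and pA and pV the rates among the rest.
- Rates over all eyes: (1−f)pA and (1−f)pV.
- Difference: (1−f)(pA − pV).
- Risk ratio: pA/pV, unchanged.
- Odds ratio for 50% vs 30%: 2.33 at f = 0, 2.21 at f = 10%, 1.89 at f = 50%.

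**4. Power (pooled chi-square form, two-sided 0.05).** Power = Φ[(d − 1.96·SE0)/SE1], with SE0 = √[p̄(1−p̄)(1/nA + 1/nV)] and SE1 = √[pA(1−pA)/nA + pV(1−pV)/nV]. The rates and f are assumptions.

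Worked case, f = 25%, 50% vs 30%:
- All eyes: 37.5% vs 22.5%, n = 93/60, d = 0.15, SE0 = 0.0770, SE1 = 0.0737. Power 49.5%.
- Eligible eyes: 50% vs 30%, n = 69.75/45, d = 0.20, SE0 = 0.0944, SE1 = 0.0908. Power 56.5%.

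| f | Difference, all vs eligible (points) | Power, all vs eligible |
|---|---|---|
| 10% | 18 vs 20 | 61.5% vs 64.6% |
| 25% | 15 vs 20 | 49.5% vs 56.5% |
| 50% | 10 vs 20 | 30.7% vs 40.5% |

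At f = 30%, rates of 35% vs 20% give 34.2% vs 37.9%, and 70% vs 50% give 39.8% vs 54.9%. Restriction raised power in every scenario tried, despite the smaller n.

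**5. Under the null.** With equal rates in both arms and f = 0, 30% and 50%, simulated type I error was 4.7% to 5.2% and the mean difference about zero.

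**6. What bounds f.** In the inferior region about half of patients should score above 1.5, that is, at least grade 2. Eyes at 0.5 can only lie in the other half. If 0-50% of that half score 0.5, f = 0.5 × (0 to 0.5) = 0-25%. Nothing in the documents bounds f in the other four regions or for lissamine.

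**7. Clearing.** Let g be the share already at 0, of whom a share s remain at 0 in both arms. The rate is g·s + (1−g)p, so the difference is (1−g)(pA − pV). Illustration with assumed g = 40%, s = 80%, 35% vs 20%: active 0.32 + 0.21 = 53%; vehicle 0.32 + 0.12 = 44%. The difference falls from 15 to 9 points and the risk ratio from 1.75 to 1.20.

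**The case against.** The strongest reply is that the all-mITT rate is a legitimate quantity for the population the SAP names. The affected eyes are balanced by randomisation, so nothing is biased under the null, and restricting to eyes able to respond answers a different question. That stands, and it is why the all-mITT rate should be kept rather than replaced.

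Other points that stand:
- A reader might infer that every affected region has no room to improve. That is true only at grade 0. An Ora region at 0.5 can improve by half a grade and can reach clearing.
- A reader might apply a large f everywhere. For the inferior region, Protocol 7.1 makes 70% untenable and 50% would need every remaining eye to score 0.5. All inferior 0.5 eyes also fall in the lower CMH stratum. A CMH simulation for that region (92 vs 60 eyes, half above 1.5, 50% vs 30%) gave 62% vs 65% at f = 10% and 52% vs 56% at f = 25%, so the gain there is small.
- For corneal sums and totals the issue should be rare, because SAP 8.1 requires an eligible eye to meet all inclusion criteria, including a score of at least 2 in a region.
- The main staining comparisons are baseline-adjusted ANCOVAs, and SAP 15 adds splits at the baseline median. These specify means and ANCOVA, so they mitigate the point but leave the responder tables unchanged. Table 14.2.20 plans responder shifts without saying which variables it covers.

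**Conclusion.** The point holds as a specification gap in secondary analyses. As written, regions that cannot meet the 1-unit definition are non-responders, and regions already at 0 can count as cleared. The exclusion of 0 and 0.5 (Ora) and 0 (Oxford) is exact. The size is not: it rests on an assumed f and assumed response rates. For 50% vs 30% the power cost is about 3 points at f = 10%, 7 at 25% and 10 at 50%, and the percentage difference shrinks by (1−f). The inferior-region range of 0-25% is itself an assumption built on the enrolment target.

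A reader might infer a biased treatment comparison, an inflated false-positive rate or a threat to the trial's main conclusions. The documents support none of these. Type I error and the 1-unit risk ratio are unaffected, the primary ANCOVAs do not use these variables, and SAP 8.5 declares all efficacy analyses exploratory.

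**What to change.** In SAP 13.2.5, 13.2.6 and 13.2.7, add a sentence on denominators for the regional responders:

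- 1-unit improvement: mITT study eyes with a baseline score of at least 1 in that region.
- Clearing: mITT study eyes with a baseline score above 0 in that region.

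Use the time-point-matched baseline of SAP 8.3, so that post-CAE results are filtered on the Day -14 post-CAE score. Show n per arm, region and time point, and report the all-mITT rate next to the restricted one. Because the filter uses only scores recorded before study treatment starts, the randomised comparison is preserved.

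The cost is one sentence in each of three sections and a filter on data already collected. The downsides are a smaller displayed n in lightly stained regions, with more recourse to Fisher's test, and a result that applies only to eyes able to respond.

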13.2.6 FLUORESCEIN CORNEAL STAINING (OXFORD SCALE)

Corneal fluorescein staining will be performed at all scheduled visits and graded using the Oxford Scale. Both pre- and post-CAE® assessments will be made at Visits 1 and 5. The Oxford scale for corneal staining ranges from 0 to 5 for the corneal region, with higher scores indicating greater staining.

Staining scores will be summarized by treatment group, visit and time point (pre- and post-CAE®) using quantitative summary statistics. Change from baseline will be also summarized. Each region and total score will be summarized separately.

Pairwise two-sample t-tests will be employed to compare treatment and vehicle means at each visit and time point. The differences in means, two-sided 95% CIs for the difference in means and p-values will be reported. Wilcoxon rank sum tests will also be conducted. Analyses will be performed on the mITT population with observed data only.

Changes from baseline will be compared between treatment groups using ANCOVA models that adjust for baseline value, baseline inferior corneal staining (Ora Calibra® scale) and baseline eye dryness (VAS). The differences in means, two-sided 95% CIs for the difference in means and p-values will be reported. T-tests and Wilcoxon rank sum tests will also be conducted. Analyses will be performed on the mITT population with observed data only.

Binary clinical cure variables will be defined by visit and region for clearing (score = 0) and 1-unit improvement (change from baseline ≤ -1), and will be summarized by visit and region using number of subjects, frequency counts and percentages. Treatment groups will be compared pairwise with vehicle using Pearson's chi-square test or Fisher's exact test if the expected cell count is less than 5 in 25% or more of the cells. In addition, the proportion of responders will be compared between treatment groups using the Cochran-Mantel-Haenszel method stratifying by baseline ICSS (≤ 1.5 , > 1.5) and baseline eye dryness (< 60 , ≥ 60). For the Cochran-Mantel-Haenszel analysis of the combined Stage 1 and Stage 2 data, the study Stage will also be included as a stratification factor.

13.2.7 LISSAMINE GREEN CONJUNCTIVAL STAINING (OXFORD SCALE)

Lissamine green conjunctival staining will be performed at all scheduled visits and graded using the Oxford Scale. The Oxford scale for conjunctival staining ranges from 0 to 5 for each of the nasal and temporal regions, with higher scores indicating greater staining. The total conjunctival score is the sum of the two regions and ranges from 0 to 10.

Staining scores will be summarized by treatment group, visit and time point (pre- and post-CAE®) using quantitative summary statistics. Change from baseline will be also summarized. Each region and total score will be summarized separately.

Pairwise two-sample t-tests will be employed to compare treatment and vehicle means at each visit and time point. The differences in means, two-sided 95% CIs for the difference in means and p-values will be reported. Wilcoxon rank sum tests will also be conducted. Analyses will be performed on the mITT population with observed data only.

Changes from baseline will be compared between treatment groups using ANCOVA models that adjust for baseline value, baseline inferior corneal staining (Ora Calibra® scale) and baseline eye dryness (VAS). The differences in means, two-sided 95% CIs for the difference in means and p-values will be reported. T-tests and Wilcoxon rank sum tests will also be conducted. Analyses will be performed on the mITT population with observed data only.

Binary clinical cure variables will be defined by visit and region for clearing (score = 0) and 1-unit improvement (change from baseline ≤ -1), and will be summarized by visit and region using number of subjects, frequency counts and percentages. Treatment groups will be compared pairwise with vehicle using Pearson's chi-square test or Fisher's exact test if the expected cell count is less than 5 in 25% or more of the cells. In addition, the proportion of responders will be compared between treatment groups using the Cochran-Mantel-Haenszel method stratifying by baseline ICSS (≤ 1.5 , > 1.5) and baseline eye dryness (< 60 , ≥ 60). For the Cochran-Mantel-Haenszel analysis of the combined Stage 1 and Stage 2 data, the study Stage will also be included as a stratification factor.

